### 5.2. Secondary Objectives

The secondary objectives are to:

1. Compare change in cumulative glucose infusion to maintain glucose at 50 mg/dL for the first 30 minutes after the 50 mg/dL is achieved.
2. Compare changes in the other counter-regulatory hormones: norepinephrine, glucagon, cortisol and growth hormone.
3. Compare changes from baseline to week 4 in subject responses to a validated hypoglycemia symptom questionnaire administered during induced hypoglycemia.
4. Compare changes from baseline to week 4 in CGM-derived hypoglycemia parameters of:
  - a. Proportional time spent with interstitial glucose < 70, 60 and 50 mg/dL.
  - b. Rate of hypoglycemic event episodes at < 70, 60, and 50 mg/dL.
5. Compare change from baseline to week 4 in CGM-derived parameters of:
  - a. Average glucose, proportional time with  $70 \leq PG < 180$  mg/dL, and proportional time with  $PG \geq 180$  mg/dL.
  - b. Plasma glucose standard deviation.
6. Describe subject reported hypoglycemic events:
  - a. Symptomatic events confirmed with self-monitored glucose < 70 mg/dL.
  - b. Symptomatic events with no accompanying glucose meter reading or a reading  $\geq 70$  mg/dL.
  - c. Asymptomatic events of self-monitored glucose < 70 mg/dL.
  - d. Severe hypoglycemia as defined by affected consciousness of hypoglycemic origin confirmed by a glucose meter reading <36 mg/dL, requiring external assistance, or prompt recovery upon hypoglycemia treatment.
7. Describe change from baseline to week 4 of unawareness measured by the Gold scale.
8. Describe basal, bolus and total daily insulin dose changes by treatment group.
9. Describe the time course of the endpoints (primary and secondary 1-7) from week 4 through the rest of the study.
10. Describe non-serious and serious adverse events by treatment group

11. Describe change from baseline through week 4 of serum concentrations of glucagon while still on the CSGI, and serum and plasma glucagon antibodies.

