#### 4.2.1 Efficacy Endpoints

- Absolute change from Induction 1 (baseline visit) to Induction 2 (visit 7, Week 4) in plasma epinephrine concentration after 30 minutes of induced hypoglycemia with PG <50 mg/dL. The average of the non-missing results at each step will be used in analysis.
- Percent change from Induction 1 (baseline visit) to Induction 2 (visit 7, Week 4) in plasma epinephrine concentration after 30 minutes of induced hypoglycemia with PG <50 mg/dL by Diabetes Duration Category (<15 years, ≥15 years). The average of the non-missing results at each step will be used in analysis.
- Intravenous glucose infusion rate (GIR) [time frame: 0-30 mins induced hypoglycemia] (cumulative glucose infusion rate required to maintain insulin-induced hypoglycemia).
- Intravenous insulin infusion rate [time frame: 0-30 mins induced hypoglycemia] (cumulative insulin infusion rate required to maintain insulin-induced hypoglycemia).
- Change from Induction 1 (baseline visit) to Induction 2 (visit 7, Week 4) in other counter regulatory hormones (norepinephrine, glucagon, cortisol and growth hormone plasma concentrations) after 30 mins of induced hypoglycemia.
- Change from Induction 1 (baseline visit) to Induction 2 (visit 7, Week 4) in Neuroglycopenic Symptom Scores (if hypoglycemia present) as documented using the hypoglycemia symptom questionnaire.
- Change from Induction 1 (baseline visit) to Induction 2 (visit 7, Week 4) in Autonomic Symptom Scores (if hypoglycemia present) as documented using the hypoglycemia symptom questionnaire.
- Change from baseline to Week 4 in CGM-derived hypoglycemia parameters of:
  - Proportional time spent with interstitial glucose (IG) <70, 60, and 50 mg/dL;
  - Rate of hypoglycemic event episodes at thresholds of plasma glucose <70, 60, and 50 mg/dL.
  - Area over the curve (AOC) of the reduction from baseline in the interstitial glucose from T0 (defined as the date/time of the CSGI injection) to Tx, where x corresponds to time when interstitial glucose < 70, <60 and <50 mg/dL is achieved.
- Change from baseline to Week 4 in CGM-derived parameters of:
  - Average interstitial glucose and standard deviation;
  - Proportional time within  $70 \leq \text{interstitial glucose} < 180$  mg/dL;

- Proportional time with interstitial glucose  $\geq 180$  mg/dL.
- Change from Induction 1 (baseline visit) to Induction 2 (visit 7, Week 4) in the Gold scale as a measure of hypoglycemia awareness.

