### 7.2.10 CGM Derived Parameters

CGM readings occur every 5 mins. Hence in a complete 24-hour period, 288 CGM readings would be captured. The following endpoints will be calculated per day (e.g., 24-hour period starting from CSGI injection).

- Proportional time spent with interstitial glucose < 70 mg/dL;
- Proportional time spent with interstitial glucose < 60 mg/dL;
- Proportional time spent with interstitial glucose < 50 mg/dL;
- Proportional time within  $70 \leq \text{interstitial glucose} < 180$  mg/dL;
- Proportional time with interstitial glucose  $\geq 180$  mg/dL.

Proportional time spent with  $IG < X$  mg/dL = (time spent with  $IG < X$  mg/dL (minutes) / total time spent with CGM (minutes)) \* 100 where  $x = 70, 60$  or  $50$ , given the continuous CGM readings.

- Rate of hypoglycemic event episodes at thresholds of plasma glucose <70 mg/dL;
- Rate of hypoglycemic event episodes at thresholds of plasma glucose <60 mg/dL;
- Rate of hypoglycemic event episodes at thresholds of plasma glucose <50 mg/dL;

Rate of hypoglycemic event episodes at thresholds of <X mg/dL is defined as the number of episodes with  $PG < X$  mg/dL, where 70, 60 or 50. Subsequent PG measures with the result of < X mg/dL should be considered as the same episode.

- Average interstitial glucose;
- Interstitial glucose standard deviation;
- Area over the curve (AOC) of the reduction from baseline in the interstitial glucose from T0 (defined as the date/time of the CSGI injection) to Tx, where x corresponds to time when interstitial glucose < 70, <60 and <50 mg/dL is achieved.

AOC calculations will be done using the standard trapezoidal rule

$$AOC = -\left(\sum_{i=0}^x \left(\frac{\text{abs}(\text{reduction in } IG_i) + \text{abs}(\text{reduction in } IG_{i+1})}{2}\right) * (T_{i+1} - T_i)\right)$$

Where:  $\text{abs}(\text{reduction in } IG_i)$  = absolute value of change from baseline in interstitial glucose at time i, and  $(T_{i+1} - T_i)$  is the Time difference in minutes between time i and time i+1.

For endpoints that will be calculated per day - baseline will be based on the CGM data collected on the latest day prior to the date/time of the first CSGI injection. For the AOC endpoint baseline will be the latest interstitial glucose measure obtained prior to the date/time of the first CSGI injection.

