**7.2.10.1 Weekly endpoints**

Additionally, all derived CGM endpoints will be derived on a weekly basis. The following weeks will be analyzed: Baseline (Week), Week 1, Week 2, Week 3, Week 4, Month 3 and Month 6. CGM-Derived parameters will be based on CGM data that fall in the following timeframe:

Week	Time window (Days)	
Baseline	7 days prior to day 1	
Week 1	1	7
Week 2	8	14
Week 3	15	21
Week 4	22	28
Month 3	7 days prior to date of Month 3 visit	
Month 6	7 days prior to date of Month 6 visit	

When deriving weekly endpoints - baseline will be based on the CGM data collected 7 days prior to the date/time of the first CSGI injection. For the AOC endpoint baseline will be the same as for the AOC calculated by day.

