### **7.10.4 Secondary Endpoints**

- Intravenous glucose infusion rate (GIR) [time frame: 0-30 mins induced hypoglycemia] (cumulative glucose infusion rate required to maintain insulin-induced hypoglycemia)
- Intravenous insulin infusion rate [time frame: 0-30 mins induced hypoglycemia] (cumulative insulin infusion rate required to maintain insulin-induced hypoglycemia)
- Change from Induction 1 (baseline visit) to Induction 2 (visit 7, Week 4) in other counter regulatory hormones (norepinephrine, glucagon, cortisol and growth hormone plasma concentrations) after 30 mins of induced hypoglycemia
- Change from Induction 1 (baseline visit) to Induction 2 (visit 7, Week 4) in Neuroglycopenic Symptom Scores (if hypoglycemia present) as documented using the hypoglycemia symptom questionnaire
- Change from Induction 1 (baseline visit) to Induction 2 (visit 7, Week 4) in Autonomic Symptom Scores (if hypoglycemia present) as documented using the hypoglycemia symptom questionnaire
- Change from baseline to Week 4 in CGM-derived hypoglycemia parameters of:
  - Proportional time spent with interstitial glucose <70, 60, and 50 mg/dL

- Rate of hypoglycemic event episodes at thresholds of plasma glucose <70, 60, and 50 mg/dL
- Area over the curve (AOC) of the reduction from baseline in the interstitial glucose from T0 to Tx, where x corresponds to time when interstitial glucose < 70, <60 and <50 mg/dL is achieved.
- Change from baseline to Week 4 in CGM-derived parameters of:
  - Average interstitial glucose and standard deviation
  - Proportional time within  $70 \leq \text{interstitial glucose} < 180$  mg/dL
  - Proportional time with  $\text{interstitial} \geq 180$  mg/dL
- Change from Induction 1 (baseline visit) to Induction 2 (visit 7, Week 4) in the Gold scale as a measure of hypoglycemia awareness

Pharmacodynamic endpoints (e.g., CGM derived parameters, counter regulatory hormones, GIR, insulin infusion rate) will be analyzed using a 1-factor (treatment) analysis of variance (ANOVA) model with treatment as the main effect.

The change from baseline for Gold scale, Neuroglycopenic Symptom Score, and Autonomic Symptom Score endpoints will be analyzed using non-parametric analysis of variance (Wilcoxon rank-sum test).

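### The CGM hypoglycemic episode count has no minimum duration and no end rule, so it is open to two readings and sensitive to sensor noise near the threshold

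*SAP*

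**What the plan says.** The protocol lists the endpoint by its thresholds only: "Rate of hypoglycemic event episodes at < 70, 60, and 50 mg/dL" (Protocol 5.2). SAP 4.2.1 repeats it as a secondary efficacy endpoint: "Rate of hypoglycemic event episodes at thresholds of plasma glucose <70, 60, and 50 mg/dL".

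The derivation is in SAP 7.2.10. On sampling: "CGM readings occur every 5 mins. Hence in a complete 24-hour period, 288 CGM readings would be captured". On the count: "Rate of hypoglycemic event episodes at thresholds of <X mg/dL is defined as the number of episodes with" a PG value below X, where X is 70, 60 or 50 mg/dL. On continuation: "Subsequent PG measures with the result of < X mg/dL should be considered as the same episode".

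That is the whole rule. It is applied per day, in 24-hour periods starting from the infusion, and SAP 7.2.10.1 extends it: "Additionally, all derived CGM endpoints will be derived on a weekly basis". SAP 7.10.4 gives the analysis: "Pharmacodynamic endpoints (e.g., CGM derived parameters, counter regulatory hormones, GIR, insulin infusion rate) will be analyzed using a 1-factor (treatment) analysis of variance". SAP 7.10.5 treats all secondary endpoints as descriptive, without multiplicity adjustment.

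**The concern.** Neither document says how many readings below X make an episode, how long glucose must be back at or above X before an episode is over, what happens when the sensor drops out, or how to count an episode that crosses a day or week boundary. Two programmers could therefore derive different values from the same trace.

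On either reading, one 5-minute value below X is enough to score an event. On the natural reading, a trace hovering at the threshold also scores repeatedly. The count then partly measures how often noise crosses a line rather than how often the subject became hypoglycemic.

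At stake is the precision of an endpoint reported at three thresholds, with 16 subjects per arm planned. The per-day baseline uses only the latest day of CGM data before the first infusion, so a few spurious counts can move a subject's change score. Protocol 6.1.2.4 expects the infusion to raise glucose, so the arms may differ in time spent near a threshold, which is where the rule is least stable.

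**Working it through.** **1. The plan's own figure.** One reading every 5 minutes gives 24 × 60 / 5 = 288 per day, as SAP 7.2.10 states, and 288 × 7 = 2,016 per week.

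**2. The rule applied by hand, X = 70.** Three versions:
- natural: a value ≥ 70 ends the episode, and the next value < 70 starts another;
- literal: every later value < 70 in the period belongs to the first episode;
- confirmed: three consecutive values < 70 to start, three consecutive values ≥ 70 to end.

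| Readings | Natural | Literal | Confirmed |
|---|---|---|---|
| 69, 71, 69, 70, 68 | 3 | 1 | 0 |
| 72, 69, 68, 71, 69, 67, 70, 68, 75, 80, 90, 69, 85 | 4 | 1 | 0 |

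The literal version cannot exceed one episode per day or per week, which leaves little for a count to measure.

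**3. Size, Gaussian dip.** The documents give no sensor-noise figure, so everything here except the 5-minute interval and the threshold is assumed. Three-hour traces. True glucose: g(t) = 100 − (100 − N) × exp(−t² / (2w²)), with nadir N and width w = 30 minutes. Reading: g(t) plus first-order autoregressive noise, SD 2-6 mg/dL, lag-1 correlation 0.5-0.8.

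For N = 66, g(t) < 70 when |t| < 30 × √(2 × ln(34/30)) = 15.0 minutes. That is seven readings (7 × 5 = 35 minutes of readings).

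| True dip | Natural: mean episodes | Natural: two or more | Confirmed: mean episodes |
|---|---|---|---|
| To 66 (one event) | 1.02-1.79 | 3-60% | 0.77-0.98 |
| To 72 (no event) | 0.25-1.22 | not tabulated | 0.02-0.36 |

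The dip width drives the result. Varying w from 15 to 40 minutes with noise SD 2 or 6 moves the chance of splitting the dip to 66 from about 0% to 79%. Slower noise reduces it: at correlation 0.9, SD 6 and w = 30, splitting falls to about 12% and the mean to 0.99.

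**4. Other shapes.** 2,000 four-hour traces per scenario. Mean count on the natural reading for one V-shaped event, nadir 60, below 70 for 60 minutes:

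| Lag-1 correlation | SD 2 | SD 4 | SD 6 |
|---|---|---|---|
| 0 | 1.60 | 2.83 | 4.02 |
| 0.7 | 1.15 | 1.66 | 2.25 |
| 0.9 | 1.01 | 1.19 | 1.43 |

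The confirmed rule gives 0.95-1.03 over the same cells. A long shallow V (nadir 66, 60 minutes below 70) is counted 1.33-7.61 times on the natural reading and 0.93-1.31 times when confirmed. Its lowest value, 1.33, is at SD 2 and correlation 0.9, so even small, slow noise splits a dip that lingers at the threshold.

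Near-misses: a 60-minute plateau at 73 scores at least one episode with probability 0.23-0.99, and a V-shaped dip to 72 with probability 0.07-0.74. These probabilities are the same on the literal reading, which removes splitting but not false starts. The confirmed rule gives a mean of 0.00-0.46 episodes on these traces.

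**5. What confirmation loses.** Gaussian dip to 66, noise SD 6, correlation 0.5-0.8. With w = 20 the dip lies below 70 for |t| < 20 × √(2 × ln(34/30)) = 10.0 minutes, or five readings (25 minutes).

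| True readings below 70 | Missed, confirmed rule | Missed, single-reading rule |
|---|---|---|
| 7 (35 minutes) | 21-23% | 1-7% |
| 5 (25 minutes) | 34-36% | 4-13% |

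**The case against.** The strongest reply is that the SAP nowhere says an episode ends at the next value above the threshold. That is correct. A reader might infer that the plan prescribes splitting, but the text is silent on the end; splitting follows only from the natural reading, and the literal one splits nothing. What stands is that the end is unspecified and that a single reading starts an episode on either reading.

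Second, the percentages are not facts about this trial. They depend on dip shape, noise SD and correlation, none of which the documents give. That stands: the direction is established and the size is conditional.

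Third, a reader might infer that the treatment comparison is biased. The documents do not show this. All arms use the same blinded recorder, the expected rise in glucose could change the noise-driven counts in either direction, and the calculations above follow single traces with no between-arm comparison. Added variance and dilution are the supportable consequences; bias is a possibility.

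Fourth, the weight is limited. The endpoint is descriptive (SAP 7.10.5), and its tables are not among those marked for the Week 4 primary-endpoint analysis (SAP 12). The indication in Protocol 6.1 concerns severe hypoglycemia, which has its own definition among the subject-reported events. Proportional time below 70, 60 and 50 mg/dL uses the same data without an episode rule. All of this stands and lowers the priority, but it does not supply the missing rule.

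Last, no document supports three readings over another number, and confirmation misses real events. Both are true; the choice is a trade-off to be stated openly.

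**Conclusion.** The point holds as an incomplete and noise-sensitive definition: one 5-minute reading starts an episode, no minimum duration is set, and no end is written. Under the Gaussian assumptions (w = 30 minutes, SD 2-6 mg/dL, correlation 0.5-0.8), a true dip to 66 is counted about 1.0-1.8 times and split in about 3-60% of cases. A dip to 72 scores about 0.25-1.2 episodes, against 0.02-0.36 with confirmation. With small, slow noise (SD 2, correlation 0.9), splitting of a clear dip is negligible.

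This should be corrected because correction is cheap. It does not touch the primary endpoint, the testing hierarchy or the proportional-time endpoints, and it is no ground for saying that the plan biases the comparison.

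**What to change.** Amend SAP 7.2.10 before any unblinding, including the group-level unblinding for the Week 4 analysis:

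- An episode starts with a fixed run of consecutive interstitial glucose readings < X (for example three, i.e. 15 minutes) and ends with a run of the same length ≥ X.
- The rule is identical at 70, 60 and 50 mg/dL and in every daily and weekly window.
- State how a sensor gap inside or next to a run is handled, and to which period an episode belongs when it crosses a day or week boundary.
- Replace PG with interstitial glucose in this definition, since that is what the CGM measures.
- Keep the single-reading count as a supportive summary if wanted, with its end rule written out.

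The cost is a few sentences and a few lines of code, with no new data. The downside is that dips shorter than the run are not counted as episodes. Under high noise (SD 6), about 20-35% of shallow true dips of 25-35 minutes are not counted either. Both remain in proportional time.

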### **6.1.2.4. Insulin Dose Adjustments**

Constant infusion of low rate of glucagon may be expected to elevate glucose not only during circumstances that may have led to hypoglycemia, but also when not needed. To avoid glycemic escape, subjects' glucose data will be reviewed weekly and insulin doses adjusted accordingly by the clinical personnel.

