## **9. STUDY PROCEDURES**

### **9.1. Outpatient Insulin Dose Adjustment During Run-in and Treatment Phases Weeks -1-4**

Subjects' insulin doses should be reviewed and adjusted to maintain current ADA recommended glycemic targets of pre-prandial PG of 80-130 mg/dL and post-prandial PG<180 mg/dL, per investigator's discretion.

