14.2.2.7.2.1*	Change from Induction 1 (Baseline visit) in Average Neuroglycopenic Scores (ANS), Average Autonomic Scores (AAS) and Average Total Scores (ATS) with PG <50 mg/dl Intent-to-Treat Population	14.2.2.7.1.1
14.2.2.7.2.2*	Change from Induction 1 (Baseline visit) in Average Neuroglycopenic Scores (ANS), Average Autonomic Scores (AAS) and Average Total Scores (ATS) with PG <50 mg/dl Per Protocol Population	14.2.2.7.1.1
14.2.2.8.1.1	Summary of Overall Assessment of Hypoglycemia with PG <70 mg/dl Intent-to-Treat Population	
14.2.2.8.1.2	Summary of Overall Assessment of Hypoglycemia with PG <70 mg/dl Per Protocol Population	14.2.2.8.1.1
14.2.2.8.2.1	Summary of Overall Assessment of Hypoglycemia with PG <50 mg/dl Intent-to-Treat Population	14.2.2.8.1.1
14.2.2.8.2.2	Summary of Overall Assessment of Hypoglycemia with PG <50 mg/dl Per Protocol Population	14.2.2.8.1.1
14.2.2.9.1.1	Change from Baseline in CGM-Derived Hypoglycemia Parameters by Day - Intent-to-Treat Population	
14.2.2.9.1.2	Change from Baseline in CGM-Derived Hypoglycemia Parameters by Day - Per Protocol Population	14.2.2.9.1.1
14.2.2.9.2.1	Change from Baseline in CGM-Derived Hypoglycemia Parameters by Week - Intent-to-Treat Population	14.2.2.9.1.1
14.2.2.9.2.2	Change from Baseline in CGM-Derived Hypoglycemia Parameters by Week - Per Protocol Population	14.2.2.9.1.1
14.2.2.10.1*	Change from Induction 1 (Baseline visit) in Gold Scale Assessment of Hypoglycemia Unawareness - Intent-to-Treat Population	
14.2.2.10.2*	Change from Induction 1 (Baseline visit) in Gold Scale Assessment of Hypoglycemia Unawareness - Per Protocol Population	14.2.2.10.1
14.3.1.1*	Overview of Adverse Events - Safety Population	
14.3.1.2*	Summary of Treatment-Emergent Adverse Events by System Organ Class, Preferred Term - Safety Population	
14.3.1.3	Summary of Treatment-related Treatment-Emergent Adverse Events by System Organ Class, Preferred Term - Safety Population	14.3.1.2
14.3.1.4*	Summary of Serious Treatment-Emergent Adverse Events by System Organ Class, Preferred Term - Safety Population	14.3.1.2
14.3.1.5	Summary of Treatment-Emergent Adverse Events Leading to Study Discontinuation by System Organ Class, Preferred Term - Safety Population	14.3.1.2

Table Number	Table Title	Shell Number (if repeat)
14.3.1.6	Summary of Serious Adverse Events Leading to Death by System Organ Class, Preferred Term - Safety Population	14.3.1.2

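### The SAP's AOC formula integrates the absolute change in glucose, so a rise above baseline scores as a reduction, and its start and stop points are missing or ambiguous in some periods

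*SAP*

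**What the plan says.** SAP 7.2.10 introduces the endpoint as "Area over the curve (AOC) of the reduction from baseline in the interstitial glucose from T0 (defined as the date/time of the CSGI injection") and runs it to Tx, the time at which interstitial glucose (IG) falls below 70, 60 or 50 mg/dL. The trapezoidal formula sums abs(reduction in IG), which it explains as the "absolute value of change from baseline in interstitial glucose at time i", and puts a minus sign in front of the sum. A more negative value therefore reads as more reduction. The reference value is a single reading: "For the AOC endpoint baseline will be the latest interstitial glucose measure obtained prior to the date/time of the first CSGI injection".

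SAP 7.2.10.1 derives every CGM endpoint, AOC included, for the Baseline week, Weeks 1 to 4, Month 3 and Month 6. For AOC it adds only that the baseline is the same as for the daily version. SAP 3.2.1, 4.2.1 and 7.10.4 repeat the definition and add no rule.

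SAP 7.10.4 says that pharmacodynamic endpoints, CGM parameters among them, "will be analyzed using a 1-factor (treatment) analysis of variance (ANOVA) model with treatment as the main effect". The table list in SAP 12 has summaries such as "Change from Baseline in CGM-Derived Hypoglycemia Parameters by Week - Intent-to-Treat Population" but names no ANOVA table for CGM. SAP 7.10.5 treats all secondary endpoints as descriptive.

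Protocol 6.1.2.4 states: "Constant infusion of low rate of glucagon may be expected to elevate glucose". As the counter-measure, "glucose data will be reviewed weekly and insulin doses adjusted accordingly by the clinical personnel"; Protocol 9.1 adds that "insulin doses should be reviewed and adjusted to maintain current ADA recommended glycemic targets".

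**The concern.** The name and the formula describe different quantities. They agree only if IG never rises above the one baseline reading between T0 and Tx. Once IG goes above it, every further rise enlarges the reported reduction. Rises are what the protocol expects glucagon to cause, so the error need not cancel between arms.

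Two limits of the integral are also incomplete. Tx has no value on a day, or in a week, without a reading below the threshold, and a treatment meant to prevent hypoglycemia may make such periods more common. T0 is tied to a CSGI injection, but some analysed windows contain none and others contain several pod starts.

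At stake is whether a secondary efficacy result can point the opposite way from what its label says, and whether two programmers would compute the same value from this text.

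**Working it through.** The documents give no AOC value, so there is no figure of the plan's own to reproduce. The checks apply the printed formula to stated, assumed inputs. Only the 5-minute reading interval comes from the SAP.

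**1. Fixed traces.** Baseline 100 mg/dL. Glucose moves to 100+h at 1 mg/dL/min, holds, is back at 100 by 565 min, then falls at 1 mg/dL/min to 65 at 600 min, the first reading below 70.

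- Excursion area: |h| x (565 - |h|). For |h| = 20: 20 x 545 = 10,900.
- Final fall: 35 x 35 / 2 = 612.5.
- SAP AOC: -(10,900 + 612.5) = -11,512.5 for both h = +20 and h = -20.
- True reduction, using max(100 - IG, 0): -612.5 for h = +20 and -11,512.5 for h = -20.

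| Held above baseline by (mg/dL) | SAP formula (mg/dL*min) | True reduction (mg/dL*min) |
|---|---|---|
| 0 | -612.5 | -612.5 |
| 5 | -3,412.5 | -612.5 |
| 10 | -6,162.5 | -612.5 |
| 20 | -11,512.5 | -612.5 |
| 40 | -21,612.5 | -612.5 |

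**2. When the direction reverses.** Suppose the change from baseline, x, is normal with mean d and SD s over a fixed window, so that there is no stopping-time effect. The mean areas per minute are

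- SAP: E|x| = s*sqrt(2/pi)*exp(-d^2/(2s^2)) + d*(1 - 2*Phi(-d/s))
- true reduction: E max(-x,0) = s*phi(d/s) - d*Phi(-d/s)

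With s = 40 mg/dL (assumed):

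| Mean change, from -> to | SAP area | True reduction |
|---|---|---|
| 0 -> +5 | 31.92 -> 32.16 (+0.8%) | 15.96 -> 13.58 (-15%) |
| 0 -> +20 | 31.92 -> 35.82 (+12%) | 15.96 -> 7.91 (-50%) |
| -10 -> +10 | 32.91 -> 32.91 (0%) | 21.45 -> 11.45 (-47%) |
| -20 -> 0 | 35.82 -> 31.92 (-11%) | 27.91 -> 15.96 (-43%) |

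The SAP area moves the wrong way when the mean starts at or above baseline, does not move when the shift straddles baseline symmetrically, and moves the right way but too little when the mean stays at or below baseline. For the shift 0 -> +20, SD 20 gives +46% against -79%, and SD 60 gives +5.5% against -36%.

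**3. Simulation over a full 24 hours.** Assumed settings: autocorrelated 5-minute readings, correlation time 60 or 120 min, SD 40 or 60, baseline uniform on 80 to 140, mean 140 in one arm and 160 in the other, 20,000 subjects per arm. The difference, raised arm minus reference arm, is -12,156 to -16,965 with abs() (apparently more reduction) and +5,084 to +7,399 with max() (less reduction, the correct direction).

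**4. Effect of the missing Tx rule.** Same settings, SAP integrand stopped at the first reading below 70. In 24 hours 0 to 21% of the reference arm and 2 to 49% of the raised arm never get there.

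- Those subjects dropped: arm difference -4,658 to -8,923.
- Those subjects censored at 24 hours: -8,556 to -24,745.

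Setting by setting, the second is 1.2 to 4.7 times the first. The SAP text permits either.

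**5. T0 by window.**

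| Window | Referent for the CSGI injection |
|---|---|
| Baseline week | None; it precedes the first pod |
| Week 1 | First pod start, Visit 3 (Protocol 9.5.3) |
| Weeks 2 to 4 | Several: a new pod at Visits 4, 5 and 6 (Protocol 9.5.4 to 9.5.6), plus changes every 2 to 3 days |
| Months 3 and 6 | None; study drug ends at Visit 7 (Protocol 9.5.7) |

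**The case against.** The strongest reply is about consequence. AOC is one of many CGM parameters, is secondary and descriptive, and has no multiplicity control. The times below threshold, time in range, mean and SD use other formulas and are unaffected. Weekly insulin review toward glycemic targets is meant to prevent sustained rises. All of this stands, and it sets the grade of the point. It does not make the formula measure a reduction.

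The second reply is that the sizes come from assumptions. That is right: no document gives a glucose rise or an SD, and the simulation places mean glucose at or above every baseline by construction. Under the stopped rule, part of the arm difference is later arrival at the threshold and not abs(). The 24-hour comparison isolates abs(), but over a window that the SAP does not use for AOC. That a rise and an equal fall score alike depends on none of these assumptions.

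A reader might infer two stronger things:

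- **That Weeks 2 to 4 contain no injection to serve as T0.** They do: Visits 4, 5 and 6 each start a new pod, and SAP 7.2.10 already counts daily periods from CSGI injection. The fault there is ambiguity.
- **That the AOC baseline reading is taken during clamp recovery.** A new sensor goes in on the morning of Visit 3 and the first pod starts during normalization, so this is possible. The documents do not say when that sensor begins recording, so it is not a demonstrated error.

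**Conclusion.** The AOC integrand is wrong as written: the SAP names a reduction and computes an absolute deviation, and no other section corrects it. The equal scoring of rises and falls follows from the formula alone. A reversed arm comparison also requires glucose at or above baseline and a difference between arms. The protocol's own expectation makes this plausible, but its size in this trial is unknown. A reader should not infer that the AOC result will be reversed; the documents support only that it can be.

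The missing Tx rule and the incomplete T0 are gaps in the same definition. Depending on how a programmer fills the first, the arm difference changes by a factor of 1.2 to 4.7 in the assumed settings. The second leaves three of the seven listed windows without a start and three more with an ambiguous one.

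This should be corrected before analysis. It does not touch the primary epinephrine endpoint.

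**What to change.** In SAP 7.2.10 and 7.2.10.1:

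1. Replace abs(change from baseline) with max(baseline - IG, 0), so that only values below baseline contribute.
2. Integrate over each full 24-hour period for every subject instead of stopping at Tx. If Tx is kept, define it as the first crossing, censor at 24 hours when the threshold is not reached, and do not drop those subjects. This second option still mixes depth of fall with time to threshold.
3. Set T0 as the start of each 24-hour period, counted from the first pod start in Weeks 1 to 4. For the Baseline week use the seven 24-hour periods before the first pod start, and for Months 3 and 6 the seven before the visit. Define weekly AOC as the mean of the daily values.

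The cost is SAP wording and a little reprogramming on CGM readings and dosing times already collected. One property should be stated in the SAP: the floored area also depends on glucose variability. With zero mean change, the formula in step 2 of the working gives s/sqrt(2*pi), or 8.0, 16.0 and 23.9 mg/dL at SD 20, 40 and 60, so arms that differ only in variability will differ in AOC.
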